 - b. Study participants who are judged to be in need of additional psychiatric or psychological evaluation/treatment, and are not currently receiving that treatment, will be referred as clinically indicated.
 - c. In addition, to minimize risk of undue anxiety related to uncertainty of diagnosis at screening we will also conduct a careful systematic diagnostic interview (the Structured Clinical Interview for DSM IV, SCID) and cognitive evaluation to determine whether there is an active diagnosable condition and provide consultation to study participants.
2. The risk that the subjects may find the study questions and procedures tedious, or that they may be distressed by the discussion of personal issues will be minimized by having a study staff person monitor the subject’s experiences during the study procedures, and by having a study clinician familiar with the participant available to assist the subject if she or he becomes distressed by study procedures. In addition, participants will be told that they may decline to answer any questions or to discuss any issue if they do not want to or if they find it distressing. Efforts will be made to make the study assessment procedures as pleasant as possible for the subject, and to detect and address any problems with evaluation procedures.
3. The risks of the blood draw include pain, bruising, and risk of infection that will be minimized by using sterile techniques, having blood drawn by an experienced phlebotomist, and offering the subject use of a topical anesthetic at the time of the blood draw.
4. To reduce the risk of side effects associated with Omega-3FA, all subjects will be educated about potential side-effects and queried about these side-effects at each weekly visit. If side-effects become too burdensome with the Omega-3FA, subjects will be offered the option of reducing the dose to one capsule rather than two per day or discontinuing the Omega-3FA altogether. It is possible that prodromal subjects taking Placebo will develop worsening symptoms and require alternate treatments for worsening mood, anxiety or psychotic symptoms. In these situations subjects will be offered treatment consistent with the standard of care in the community.
5. To reduce the risk of heavy metal and toxin contamination in the Omega-3FA, the company we have selected to provide the Omega-3FA performs their own screening (Ocean Nutrition Canada) and we will also use an independent laboratory to assure the levels of Omega-3FA in capsules, their stability in capsules, and the absence of any contaminants, including toxic substances in this product. Stability and toxicology testing will be provided by Siliker Canada Co.

6. In order to minimize subject discomfort and attrition, it will be important to reduce the burden of participation in the study. The full clinical assessment will take about 2 hours. Within the constraints of the research design, efforts will be made to accommodate participants' schedules and, when indicated, to avoid fatigue. Investigators from the participating sites will evaluate subject burden on an ongoing basis and adjust the assessment schedule uniformly across sites in the event any problems arise.
7. Procedures for the management of anticipated clinical issues include the following:
 - a. If the screening visit the subject that is found to have a medical condition that may have caused the prodromal or psychotic symptoms, they will be excluded from further participation. If either an exclusionary medical condition or an incidental medical condition is suspected, the participant will be advised to consult with their physician or will be provided with referral information. If a psychiatric disorder is found to be present at baseline, or is found to develop during the course of the study participants would be advised to consult with their mental health care provider or provided with referral information for treatment. These participants will continue to be followed in the study, with information on treatment recorded in the database.
 - b. Minor subjects and their parents or guardians will be informed that we will be doing urine drug screens as part of the routine study evaluations. We will explicitly inform parents and potential minor subjects, in the written informed consent document and orally, that we will not inform the parent of the results of the drug test, because revealing this information could affect the willingness of the minor subject to participate in the study or answer truthfully. We will tell both the minor subject and the parent or guardian our clinical policy regarding confidentiality, as follows: If a minor subject is found to have a positive drug screen, the PI will discuss the risks of drug use with the subject, and encourage the minor subject to discuss their use of drugs with their parent or guardian. If the subject is found to have a substance use disorder, we will discuss the need for treatment with the subject, and encourage the subject to allow us to speak with their parent or guardian about our concerns.
 - c. Participants who are minors will be informed that their parent will be notified in the event that they are engaging in or plan to engage in behavior (i.e., suicidal attempt) that is dangerous to themselves or others.
 - d. To summarize, our procedures will follow routine clinical research procedures to reduce risk to participants, and follow all State regulations regarding treatment of minors and informing parents and guardians. A single clinician will attempt to engage the minor in a therapeutic relationship, and maintain confidentiality unless there is a specific, immediate safety risk (e.g., suicidal ideation).

Data and Safety Monitoring Plan: All studies conducted at this site are reviewed and approved by an Institutional Review Board (IRB). A signed informed consent, assent (as applicable), and HIPAA Authorization form is obtained from the subject or the subject's legally authorized representative prior to the initiation of any study related procedures. Handling, dispensing and administration of the investigational drug must be in accordance with all state and federal laws and regulations. The IRB requires regular updates on the status of research projects, including the number of participants enrolled, adverse events or unanticipated problems, number of withdrawals from the project, complaints about the research, and any protocol changes. Any significant adverse events (which will be reported to the IRB as soon as possible, never to exceed 10 days from when the adverse event becomes known to the PI or study staff). The IRB also monitors the consent forms and ensures that appropriate HIPAA information is included.

Adverse events in this research project are expected to be uncommon. However, should we find that a participant has an adverse event we will take the appropriate steps to deal with the issue. Staff will consult with the study physician and the PI and address patient safety. Any possible serious adverse events will be reported to the PI immediately. In addition, the PI will conduct a safety review at a weekly frequency. All subjects will be reviewed at a regularly scheduled weekly meeting and any adverse events will be discussed. Adverse events will be defined as any adverse occurrence between the signing of consent and 2 weeks after the end of study.

participation. Unanticipated risks are those risks not cited in the protocol or known risks of the illness under study. Unanticipated risks include instances where anticipated risks exceed expectations in terms of their magnitude or frequency.

The Principal Investigator will attribute adverse events as follows:

- Definite: Adverse event(s) will clearly be related to investigational agent(s) or other intervention
- Probable: Adverse event(s) will likely be related to investigational agent(s)
- Possible: Adverse event(s) may be related to investigational agent(s)
- Unlikely: Adverse event(s) will doubtfully be related to investigational agent(s)
- Unrelated: Adverse event(s) will clearly not be related to the investigational agents(s)

A serious AE will be one that results in death or the immediate risk of death, hospitalization or the prolonging of an existing hospitalization, persistent or significant disability/incapacity or a congenital anomaly/birth defect. Adverse events will be graded as follows:

- No adverse event or within normal limits
- Mild adverse event
- Moderate adverse event
- Severe adverse event resulting in hospitalization or prolongation of existing hospitalization, a persistent or significant disability/incapacity, or a congenital anomaly/birth defect.
- Life-threatening or disabling adverse event
- Fatal adverse event

The principal investigator will evaluate the adverse event and determine whether the adverse event affects the Risk/Benefit ratio of the study, whether the blind should be broken, and whether modifications to the protocol (at Risks to Subjects, or in Procedures) or consent form (at Risks and Inconveniences) are required. Serious unanticipated adverse events will be reported within 24 hours to the local IRB, the FDA, and NIMH if unblinded on treatment course (vs. placebo), unless the attribution is that the adverse event is unrelated to study participation. Either the principal investigator or the RCP have the authority to stop or suspend the study. A summary of the adverse events will be reported to the RCP when reapproval of the protocol is sought. The summary will include number of subjects enrolled and a summary of graded adverse events to date.

We will also utilize a Data and Safety Monitoring Board (DSMB) that is already established at our Center. The Center has a system for appropriate oversight and monitoring to ensure safety and welfare of the participants and validity of the data in the form of a DSMB for studies conducted through the Center. The DSMB has one face-to-face meeting and at least three conference calls every year. This study will be reviewed three times a year by the DSMB. Their review/monitoring will include reviewing the protocol, risk:benefit considerations, informed consent documents and plans for data safety and monitoring; evaluating the progress of the study, including periodic assessments of data quality and timeliness, participant recruitment, accrual and retention; and other factors that can affect study outcome; considering factors external to the study such as scientific or therapeutic developments that may have an impact on the safety of the participants or the ethics of the study; protecting the safety of the study participants and reporting on the safety and scientific progress of the trial. The DSMB has the power to recommend to the PI that the study be stopped or modified.

Confidentiality: Confidentiality will be maintained by assigning each patient a study number, and coding all data collected with that number. Identifying information will not be stored on computer databases, and will not be stored with the study subject number. All computer databases are password protected, and hard copies of all data and records will be stored in locked filing cabinets. We will further protect subject confidentiality by seeking a Certificate of Confidentiality to protect the sensitive clinical information and urine drug screen data from legal discovery. All study personnel will be certified to conduct research with human subjects, and will be aware of the importance of maintaining strict confidentiality.

In Case of Injury: If a subject experiences a research injury, the site PI or designee will provide or arrange for medical treatment. This treatment will be offered for any physical injuries sustained as a consequence of participation in this research. However, UCLA will not be responsible for payment for such treatment.

References

1. Bazan NG. Lipid signaling in neural plasticity, brain repair, and neuroprotection. *Mol Neurobiol*. Aug 2005;32(1):89-103.

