Procedures

During the week prior to randomization and beginning study capsules, patients will undergo eligibility and baseline examinations. After beginning study capsules, patients will be scheduled for 6 monthly follow-up visits as well as 12-, 18-, and 24-month follow-ups (Table 1).

Omega-3FA and Placebo: The Omega-3FA compound will be manufactured by Ocean Nutrition Canada and contain an 2:1 proportion of EPA to DHA in which each capsule includes 370 mg EPA and 200 mg DHA as well as 2 mg/g Tocopherol. The dose will be two capsules per day for a total of 740 mg of EPA and 400 mg of DHA. The ratio and dose of Omega-3FA were selected based on previous data from controlled trials that demonstrates the efficacy of EPA in trials with schizophrenia patients^{37, 38} and the potential benefit of a low dose of DHA in combination with EPA per the Amminger study⁶⁰ in prodromal patients. The placebo is a soybean/corn blend. Both the Omega-3FA and placebo are colored with carob (so shell is brown) and flavored with natural lemon-lime, to mask them. Certificates of analysis for the Omega-3FA and placebo compounds are included in the Appendix. Ongoing testing by independent laboratories will assure the levels of Omega-3FA in capsules, stability, and absence of any contaminants, including toxic substances in this product. Stability and toxicology testing will be provided by Siliker Canada Co. UCLA will receive the compounds and assign coded numbers to packets before distribution to sites and thereby administer the double blind design.

Antipsychotics: Prodromal patients currently on anti-psychotic medication will be excluded from the study. It is possible that prodromal subjects will develop worsening symptoms and require such treatments during the course of the trial, which is allowed. All concomitant treatment will be recorded.

Antidepressants: Prodromal patients currently on anti-depressant medication will be included in the study; randomization to Omega-3FA vs placebo will be stratified on anti-depressant medication status.

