Vital signs & weight	X		X	X	X	X	X	X	X	X	X	
Labs (LFTs etc)	X				X			X				
Adverse events	X	X	X	X	X	X	X	X				
Treatment Logs	X	X	X	X	X	X	X	X	X	X	X	
Clinical Outcomes												
SOPs		X	X	X	X	X	X	X	X	X	X	
SCID		X							X	X	X	
SCID-SPD		X							X	X	X	
Depression (CDSS)	X	X	X	X	X	X	X	X	X	X	X	
GAF	X	X	X	X	X	X	X	X	X	X	X	
GF-Social	X	X	X	X	X	X	X	X	X	X	X	
GF-Role	X	X	X	X	X	X	X	X	X	X	X	
Other Outcomes												
Neuropsychology		X						X	X		X	
Brain imaging		X						X	X		X	
Electrophysiology		X						X	X		X	
Salivary cortisol		X							X		X	
DNA/RNA/plasma		X							X		X	

Key: X=Existing Protocol; X=Added for Omega3 Trial

Concomitant Medications: Subjects may continue doses of antidepressant, mood stabilizer, or stimulant medication as prescribed independently of their participation in this trial. Antipsychotic medication will not be permitted unless subjects develop worsening symptoms and require antipsychotic medication during the course of the trial. All concomitant treatment will be recorded.

Concomitant Psychotherapy: During the 6-month active treatment phase, all subjects will receive up to 6 sessions of supportive case management, as needed, as part of their evaluations by psychological staff. Staff members will provide support and address the young person's efforts to cope with symptoms and functional deficits. In addition, subjects will be permitted to participate in any outside of study supportive psychotherapy, with all concomitant psychological treatments recorded.

Family Focused Treatment (FFT) Study: Patients enrolled in the FFT study will be stratified prior to randomization in the Omega-3 trial, such that equal numbers of FFT participants will be assigned to the Omega-3FA and placebo groups. About one-quarter of the patients enrolled in NAPLS participate in the FFT study. Because the enrollment period for the FFT study will end on December 31, 2011, only about one-third of the participants in the Omega-3 trial would actually be eligible to participate in both studies. Thus, the overlap between patients participating in the FFT and Omega-3 trials is expected to be less than 10% (i.e., .33 x .25 = .083). Given this, we do not expect to have sufficient numbers of cases enrolled in both studies to be able to test whether participation in one moderates effects of participating in the other, but stratified group assignment

will ensure that equal numbers of cases in active treatment and control conditions are balanced for FFT participation.

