For minors, a parent/legal guardian may provide additional information useful for clinical or historical data. Written and oral consent will be obtained from participants, or their legal guardian for minor participants. Assent will be obtained from minors. Only study personnel directly associated with the research will have access to individually identifiable information.

Power Calculations and Statistical Analyses

Over the 16-month enrollment period, a total of 128 patients will be consented and randomized to receive Omega-3FA or placebo for 6 months. This number is half of the expected enrollment in NAPLS during that period, leaving room for a refusal rate of 50%. Of the 128 subjects randomized (64 to Omega-3FA, 64 to placebo) based on the retention rate in the Amminger et al. and similar studies with Omega-3FA, about 102 would be expected to complete the trial (51/51). Amminger et al. found that patients on placebo were 5.6 times more likely to convert than those on Omega-3FAs (i.e., 27.5/4.9). In the proposed study, given an initial sample size of 128, a 20% attrition rate, and a 12-month conversion rate of 22% in the placebo group (as was detected in NAPLS 1), we have 80% power to detect as significant at alpha=0.05 a hazard rate of 4.9 (i.e., corresponding to a conversion rate of 4.5% in the Omega-3FA group). However, power will be lower than 80% if the observed relative risk is less than 4.9; for example, power falls to .61 when the hazard rate is 2.8, or 50% of that observed in Amminger et al.). Note that the 22% baserate of conversion to psychosis over 12-months in NAPLS I was based on patients who received a variety of treatments, including psychosocial and pharmacological, in the community. In addition, after accounting for attrition, we have 80% power to detect a difference in functional outcome or symptom scores of 0.49 standard deviation units or greater. Amminger et al. observed effects larger than .49 on measures of symptoms and functioning, suggesting that power to detect effects on continuous measures of symptoms and functioning in the proposed study is quite favorable.

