For evaluation of the primary outcome measure (time to conversion), we will use Cox's proportional hazards model and Kaplan-Meier survival analysis as implemented in SAS PROC PHREG and LIFETEST. The secondary and tertiary outcome variables, all treated as continuous variables, will be examined as a function of treatment condition and site using mixed effects regression models. Mixed effects models permit the estimation of symptom trajectories at the level of the individual participant over time. Then the random coefficients from these within-participant trajectories are modeled as a function of treatment condition and appropriate baseline covariates (e.g., initial severity of symptoms; age or gender). At the level of the individual participant, time-varying covariates (e.g., antipsychotic treatment or not) can also be controlled, thus permitting the estimation of within-participant trajectories over and above any time-varying covariates. Similar approaches will be used to examine the trajectory of functional outcome scores. The advantages of mixed effects models over traditional repeated measures models are that they allow for (1) the inclusion of participants with missing data, (2) observations that are unequally spread out over time (both within and between participants), and (3) more flexible modeling of variance and covariance patterns of residuals. We will use two programs – SAS PROC MIXED and MIXREG – to examine these models.

Human Subjects

Only participants who meet eligibility criteria for and have previously been consented for the North American Prodrome Longitudinal Study (NAPLS) will be invited to participate. Participants will thus include individuals who are referred or respond to announcements because they may be experiencing symptoms that are associated with the prodrome of psychosis. These individuals will be referred by community health care providers or will be self-referred in response to media announcements or internet searches. Recruitment involves providing announcements to local primary care practitioners, including community pediatricians, family practice physicians, local clergy, educators, clinical social workers, psychologists, and psychiatrists. This information will include a letter introducing the study, and a brochure that describes prodromal symptoms.

Based on enrollment in NAPLS to date, about 65% of the sample are expected to be males. About 20% of subjects are expected to be African American and about 10% Latino.

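### Randomisation is stratified on antidepressant status and FFT participation, but the analysis text names neither; stratifying the primary test by antidepressant status would be a small, free improvement

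*Combined protocol and SAP*

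**What the plan says.** Two factors constrain the allocation. Under Procedures, the Antidepressants paragraph states that "randomization to Omega-3FA vs placebo will be stratified on anti-depressant medication status". The Family Focused Treatment (FFT) Study paragraph states: "Patients enrolled in the FFT study will be stratified prior to randomization in the Omega-3 trial". That paragraph adds that the "overlap between patients participating in the FFT and Omega-3 trials is expected to be less than 10" per cent, worked there as .33 × .25 = .083. On testing whether one treatment moderates the other, it says "we do not expect to have sufficient numbers of cases enrolled in both studies", and it relies on balanced assignment instead.

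The only analysis text is in Power Calculations and Statistical Analyses. For time to conversion it names the "proportional hazards model and Kaplan-Meier survival analysis as implemented in SAS PROC PHREG and LIFETEST", with no stratum or covariate. The secondary and tertiary outcomes "will be examined as a function of treatment condition and site using mixed effects regression models". Baseline covariates may be added to those models. Initial severity, age and gender are given as examples, and neither stratification factor is among them.

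**The concern.** A factor used to balance the arms is normally also used in the analysis. Stratified allocation makes the arms more alike on that factor than simple randomisation would. If the factor predicts outcome, an analysis that ignores it overstates the chance variation between arms and is somewhat conservative.

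For FFT the protocol explains its reliance on balance. For antidepressant status it gives no comparable explanation and does not say whether the primary test uses the factor. Power is the thing at stake: only about 16–18 conversions are expected, and the plan itself puts power at .61 for a ratio of 2.8.

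**Working it through.** **The plan's own figure.** The power section assumes "a 12-month conversion rate of 22% in the placebo group", 4.5% on Omega-3FA, 51 completers per arm and alpha .05 (sidedness not stated; two-sided used here). The arcsine formula is power = Φ(h·√(n/2) − 1.96), with h = 2·asin√.22 − 2·asin√.045 = .549. It gives Φ(.549 × 5.05 − 1.96) = .792, against the stated 80%.

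**Primary outcome: inputs for the simulation.**
- From the protocol: 128 patients, 1:1 allocation, 22% placebo conversion at 12 months, 20% drop-out, FFT share 8.3%. The plan's 2.8 and 4.9 are used as treatment hazard ratios (HR).
- Assumed, because the protocol does not give them: antidepressant prevalence 20–60%; HR for conversion between users and non-users (factor HR) of 1, 2 or 4; permuted blocks of 4 within antidepressant × FFT strata; exponential event times; drop-out uniform over 12 months.

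The unstratified log-rank test uses Z = (O − E)/√V over all patients. The stratified test uses Z = Σ(Oₛ − Eₛ)/√ΣVₛ over the two antidepressant strata. Both reject at |Z| > 1.96. There were 20,000 trials per setting; the Monte Carlo standard error is about 0.35 points for one power and 0.06–0.16 points for a paired difference.

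Power, unstratified → stratified by antidepressant status:

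| Treatment HR | Factor HR | Prevalence 20% | 40% | 60% |
|---|---|---|---|---|
| 2.8 (about 18 events) | 1 | – | .534 → .533 | – |
| 2.8 | 2 | .525 → .532 | .529 → .536 | .530 → .534 |
| 2.8 | 4 | .518 → .546 | .508 → .537 | .520 → .541 |
| 4.9 (about 16 events) | 1 | – | .799 → .798 | – |
| 4.9 | 2 | .800 → .803 | .798 → .803 | .799 → .803 |
| 4.9 | 4 | .794 → .810 | .793 → .813 | .802 → .811 |

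From these rounded powers, the change is −0.1 point at factor HR 1. At factor HR 2 it is +0.4 to +0.7 (treatment HR 2.8) and +0.3 to +0.5 (4.9). At factor HR 4 it is +2.1 to +2.9 and +0.9 to +2.0.

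Type I error, unstratified / stratified:
- factor HR 1: .047/.047 (40% prevalence)
- factor HR 2: .048/.050, .049/.052, .048/.049 (prevalence 20, 40, 60%)
- factor HR 4: .039/.053, .041/.052, .044/.050 (same order)

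A repeat with 8,000 trials per setting at 40% prevalence agrees. At treatment HR 2.8 it gave .527/.527, .525/.534 and .507/.536 for factor HR 1, 2 and 4. At 4.9 it gave .801/.800, .805/.806 and .798/.814. Unstratified type I error was .051, .047 and .038.

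**How far to stratify.** FFT: .083 × 128 = 10.6 patients, with 1.5 conversions expected at treatment HR 2.8 and 1.3 at 4.9. Adding FFT to the strata changed power by −0.7 to 0.0 points. Site: with 102 patients and 51 × (.22 + .045) = 13.5 events, crossing antidepressant status with the 8 sites cut power from about .78–.80 to .69–.72. Adding FFT to that cut it to .66–.68.

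**Continuous outcomes.** The plan claims "80% power to detect a difference in functional outcome or symptom scores of 0.49 standard deviation units or greater". Take d = .49, 51 per arm and se = √(2/51) = .198. Suppose the balanced factor explains a share R² of the variance.
- Unadjusted power = Φ((d/se − 1.96)/√(1 − R²)).
- Adjusted power = Φ(d/(se·√(1 − R²)) − 1.96).
- R² = .01: .697 → .701 as printed, a gain of 0.3 points before rounding. R² = .02: .698 → .705, a gain of 0.7 points.
- The unadjusted standard error is too wide by 1/√(1 − R²) − 1, which is 0.5% and 1.0%.

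With prevalence p, q = 1 − p and a difference of δ SD between users and non-users, R² = pqδ²/(1 + pqδ²). At p = .4, δ = .2 and .3 give 1.0% and 2.1%. An R² of 5–10% would need about .5–.7 SD and would gain 1.7–3.5 points. That is an upper range, likely lower once baseline severity is in the model. The formula treats the outcome as a single two-arm comparison, so it only approximates the mixed model.

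**The case against.** The strongest objection is that, in the primary test, stratifying adds no information. Comparing the tests at equal true size (12,000 trials per setting, treatment HR 2.8), unstratified and stratified power were:
- factor HR 2: .544/.544 at 20% prevalence and .533/.530 at 40%
- factor HR 4: .552/.551 and .551/.535

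This stands. The gain at the 1.96 cut-off comes from bringing a conservative test back to its nominal level. It is still a real gain in practice, because the trial will be judged at the nominal level.

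It is also fair that no figure in the protocol supports a strongly prognostic factor, that block size is not given although the conservatism depends on how tightly arms are balanced within strata, and that the open covariate list already lets both factors into the mixed models. These points lower the priority. They do not settle what the primary test will be.

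Four stronger readings are tempting, and the protocol does not support them:
- **Type I error is inflated, or the comparison is invalid.** The simulated unstratified rate was about .05 or lower throughout.
- **The sponsor chose an unadjusted analysis.** The text is silent, which is under-specification and not a decision.
- **Every randomisation factor should become a stratum of the primary test.** With so few events, FFT adds nothing and site costs power.
- **The weakness of Wald tests belongs here.** At treatment HR 2.8 (40% prevalence, factor HR 2) the unadjusted Wald test has .480 power against .529 for the unstratified log-rank. That loss comes from few events and is a separate matter.

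**Conclusion.** The point holds as a minor, free improvement and is not a validity fault. Both factors are used in allocation and neither is named in the analysis. For the primary test the consequence is slight conservatism, and only if antidepressant status is prognostic. At factor HR 2 the error rate (.047–.049) is hardly distinguishable from that seen with no prognostic effect (.047 and .051 in the two runs). It is clearly below nominal only at HR 4, an upper end. The recoverable power is under 1 point at HR 2 and about 1–3 points at HR 4. Precision in the strict sense improves only for the continuous outcomes, by 0.3–0.7 points of power at 1–2% of variance explained. All sizes rest on the assumed prevalence, prognostic strength and blocks of 4. The priority is optional.

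**What to change.** In Power Calculations and Statistical Analyses, before unblinding, state that:
1. the primary test of time to conversion is stratified by antidepressant status at randomisation, and by that factor alone;
2. it is not crossed with site or FFT, because only about 16–18 events are expected;
3. the unstratified result is reported as a sensitivity analysis;
4. the SOPS and functioning mixed models include antidepressant status as a fixed effect alongside site.

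FFT participation may also be added to the mixed models, but with about 11 patients it offers little.

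The cost is a sentence or two of text. Antidepressant status is already known at randomisation, so no patients, visits or data are added. If it proves not to be prognostic, the expected loss is about 0.1 point of power, within simulation error.
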